10.2. Twelve Month Post-Operative CT Scan

One of the secondary outcome measures in ROCSS is the presence of a hernia on CT scan at 12 months post randomisation. For these purposes, a hernia will be defined as any evidence of a defect present in the abdominal wall (see above: Definition of a hernia). A time frame of +/- 3 months from this 12 month time point is acceptable.

It is expected that the majority of trial participants will have had a stoma for colorectal cancer. In this group of patients, a one year post-operative abdominal/pelvic CT scan to assess for cancer recurrence is routine in the UK. This CT scan will be performed as a standard CT scan of the abdomen and pelvis as per the participating hospital's local protocol using a maximum slice thickness of 5mm. This routine scan will be used to assess for hernia recurrence instead of arranging a study one-year post-randomisation scan. In exceptional cases, an MRI scan as per participant's hospital local protocol may also be used to assess for hernia recurrence for patients undergoing surgery for cancer.

Non-cancer patients who have a stoma for a benign condition (such as Crohn's disease) usually do not routinely require CT follow up. These patients thus need an additional CT scan at one year to assess for hernia recurrence. This CT can be performed in one of the following two ways:

- 1. **Standard low dose CT KUB protocol**: (to detect renal tract calculi) using no oral contrast, no IV contrast and a maximum slice thickness of 5mm, so enabling a lower radiation dose exposure.
- 2. Limited CT scan protocol: For those patients who are having a CT scan that would not normally be performed (i.e. a stoma originally placed for benign disease) a local centre may choose to follow a low radiation dose protocol. This should be performed as follows:
 - i. No IV or oral contrast is required.
 - ii. Instead patient drinks 1L of water over 45 minutes (flavoured if desired).
 - iii. Low dose scan (same as the local institution's CT-KUB protocol).
 - iv. Stoma site identified visually on the skin and a marker placed (e.g. a thin paper clip).
 - v. Scout scan of abdomen performed.
 - vi. This is used to plan the axial slices in which a block 10cm above and 10cm below the skin marker (but no lower than pubic symphysis) is acquired. This is to take into account that the skin closure site may not correspond to the abdominal muscle closure site, particularly in obese trial participants).
 - vii. The skin marker is removed (in order to avoid streak artifact).

- viii. The planned axial slices are acquired.
- ix. The images are reviewed by the CT radiographer. They may choose to extend the acquisition to include areas of interest in the abdominal wall not fully included on the scan.

A named local radiologist will be involved at each site to provide local reports which maintain local clinician blinding to placement of mesh.

CT scans will be performed at local centres and then centralised for review by two blinded radiologists. The scans will be transferred either by electronic systems if available or by a compact disc to the BCTU. The radiologists will use a standardised CRF to review the CT scans. No direct involvement is required from radiologists at local centres. The local PI and registrar teams will organise the scans. Transfer will be organised with the help of local radiologists.

10.3. Ultrasound Sub-study

One of the secondary outcome measures in this study is to evaluate the detection rate of stoma site hernias with a CT scan at one year. This CT is performed as a 'standard' scan, in a supine position with the patient holding their breath. It is possible that this CT scan will not detect abdominal wall hernia owing to the lack of a 'dynamic' element. In order to address this concern, we propose using ultrasound to scan 40 consecutive patients who have undergone their one year follow-up CT scan in the Queen Elizabeth Hospital Birmingham as part of the ROCSS trial.

This sub-study is described in detail in the sub-study protocol that can be found in the appendices.

10.4. Pilot Patient Incentive Scheme

A pilot scheme is to be introduced to a number of sites in the UK to see if patient incentives improve uptake of 24 month follow up visits in those patients that have not withdrawn from the study but failed to attend after the initial invitation.

- Patients that have failed to attend their initial 24 month follow up visit will be offered a small gratuity in the form of a gift card for twenty pounds when re-arranging their 24 month follow up. Sites will be provided with a complimentary slip that they may use for patients to offer this gratuity.
- This offer of a gratuity will be given to patients at attendance of their 24 month follow up assessment.

Patients will not be offered any form of payment at initial contact discussing the upcoming 24 month follow up assessment nor given to those patients who attend their 24 month follow up after initial invitation.

10.5. Patient Withdrawal

Patients may withdraw from the trial at any point. Within ROCSS there are different types of withdrawal, if a patient decides to withdraw the details should be documented in the medical notes and the ROCSS trial office informed.

The types of withdrawal in ROCSS are:

- Withdrawal from trial-specific follow-up: the patient has had trial treatment but does not wish to be followed up according to the protocol. The patient will be followed up according to standard practice. It must be confirmed that the patient has agreed that follow-up data collected at standard clinic visits may be used in the final analysis.
- Total withdrawal from the trial: the patient is not willing to be followed up for trial purposes at any further visits, i.e. only data collected prior to the withdrawal of consent can be used in the final analysis.

All patients are analysed on an Intention-To-Treat basis, therefore all patients are followed within the trial, regardless of receipt of randomised allocation, unless the patient withdraws consent.

10.6. Unblinding of patients

Patients will be asked to complete a "Patient Allocation Request" form providing consent for the ROCSS study office to directly send the patient their randomisation allocation. Patients wishing to be notified of their randomisation prior to completing the study may do so by written request directly to the ROCSS team at BCTU.

By the ROCSS study office corresponding directly with the patient, it will ensure that sites remain blind to randomisation allocations.

The Patient Allocation Request form will be completed at the patient's next follow up appointment or sent a letter via post.

In ROCSS-EX, this process is streamlined for patients. If they request to be informed of their allocation during the telephone consultation, they will be asked to provide contact information (email or postal address), which will be submitted to the trial office along with the follow-up data. Once the data collection period has ended and the database has been locked, the patients who have requested to be told their randomised allocation will be informed.

10.7. Compliance with the Protocol

The investigators and sponsor will agree to implement the study protocol as written. The study will be performed in accordance with the Declaration of Helsinki, International Committee on Harmonisation of Good Clinical Practice Guidelines and the local laws and recommendations recommended by the European Community.

10.8. End of Trial

The end of the trial for regulatory purposes is defined as 6 months after the date of the last clinical follow-up appointment of the last patient undergoing protocol based treatment.

10.9. Trial Extension

The main results from ROCSS have now been published¹⁵. The results indicate a significant reduction in the rate of incisional hernia after reinforcement of the stoma closure site with biological mesh. However, they do not show a benefit to the patient in terms of quality of life or to the NHS in cost.

A 5-8 year follow-up will take place to investigate these outcomes and is described fully in Section 19.

11.Recruitment

11.1. Projected Recruitment Schedule

One of the main aims of the feasibility study was to assess the ability to recruit patients into the trial. The feasibility study aimed to recruit 90 patients over 12 months. This was achieved ahead of schedule and we have now continued into the main phase III trial, where the aim is to randomise a further 470 patients to a total of 560 patients. The recruitment projection is that this will take 2.5 years in total. We are aiming to recruit patients from at least 30 units across the United Kingdom.

The projected recruitment is:

- Feasibility Study: 90 patients
 - Months 1-12: 5 centres at rate of 1 patient/ month for 12 months = 60 patients
 - Months 6-12: 5 additional centres at rate of 1 patient/ month for 6 months = 30 patients

- Phase III trial: 470 patients
 - Months 12-30: 10 centres at rate of 1 patients/ month for 18 months = 180 patients (note: these will be centres from the feasibility study)
 - Months 12-30: 10 further centres at rate of 1 patient/ month for 18 months = 180 patients
 - Months 18-30: 10 new centres at rate of 1 patient/ month for 12 months = 120 patients
- If recruitment is ahead of target, the sample size of the phase III study will be increased to 790, which would provide 90% power to detect a 40% reduction in 2 year clinical hernia rate.

11.2. Screening Logs

As part of ROCSS, a screening log of potentially eligible patients will be kept by all participating centres.

Screening logs should be kept of those patients who are potentially eligible for entry into the trial i.e. those patients undergoing stoma reversal, but who are subsequently not randomised, missed or refuse randomisation. The reason for non-inclusion should also be documented.

A recruitment contact at site should be nominated; the ROCSS Study Office will request this information on a monthly basis.

12.Safety Monitoring Procedures

12.1. Serious Adverse Events

A Serious Adverse Event (SAE) is any untoward medical occurrence which:

- Is fatal or immediately life-threatening (the patient was at risk of death at the time of the event). This does not refer to an event that hypothetically might have caused death if more severe.
- Requires or prolongs hospitalisation.
- Results in persistent or significant disability/incapacity.
- Is a newly identified cancer.

Stoma site closure specific SAEs include, but are not limited to:

- Unexpected events occurring during the surgical intervention e.g. excess wound infection, excess wound breakdown, abscesses associated with the mesh.
- Postoperative pain above that normally expected following the surgical intervention.

Note that within ROCSS, hospitalisation for elective surgery is NOT considered to be an SAE.

12.2. Recording and Reporting Serious Adverse Events

The Investigator must report in detail all SAEs believed to be due to surgery or the use of the biological mesh.

SAE recording shall begin as soon as the patient signs the Patient Consent Form. All SAEs will be collected for all patients in the study and must be recorded on the SAE form and faxed to the BCTU on [name] as soon as site staff become aware of the event.

Details recorded for each Adverse Event will include:

- nature of the sign or symptom
- date of onset
- date of resolution (duration)
- the severity
- the relationship to study treatment or other therapy

- the action taken (if any)
- the outcome

SAEs still present at the end of the study must be followed up at least until the final outcome is determined, even if it implies that the follow-up continues after the patient's study participation is complete and, when appropriate, until the end of the planned follow-up period of the study.

12.3. Timeframe for reporting SAEs

Any event that satisfies the SAE reporting criteria/ are to be reported for all patients in the study from trial entry to the 30 days post-operative review .. After this 30 days post-operative time point and until the completion of the 24 month follow up only events satisfying the SAE reporting criteria **and** pertaining to the abdomen should be reported.

12.4. Responsibilities for Reporting of SAEs

The BCTU will report all SAEs to the DMEC at regular intervals (at least annually), and to the main REC annually. Local Investigators are responsible for reporting SAEs to their host institution, according to local regulations.

13.Sample Size, Statistics and Data Monitoring

13.1. Sample Size

Current data (as identified through a systematic review of the published literature) is heterogenous due to reports from diverse study populations with incomplete follow-up. Many studies showed low herniation rates due to no clinical follow-up, where they were based on patient reports.

The sample size calculation was therefore based upon studies with active follow-up where hernia was a primary endpoint, which showed higher hernia and re-operation rates²⁻⁴. In these studies, the clinically detectable hernia rate was over 25%. To detect a 40% reduction in 2 year clinical hernia rate (i.e. from 25% to 15% with the biological mesh) requires 500 patients (250 in each arm, with 80% power, alpha=0.05). This was increased to 560 patients (280 per arm) to allow for a 10% drop-out rate. Prophylactic mesh placement for other types of hernia (such as parastomal hernias) has shown reductions of between 40-100%^{12 13 16}, so this reduction sits at the cautious end of the range.

As recruitment is ahead of target, the power of the study may be increased to 90% with 15% drop-out (rather than 10%, to also account for patients who won't contribute to the primary outcome as they have not had their stoma reversed). To detect a 40% reduction in 2 year clinical hernia rate with 90% power requires 670 patients, increasing to 790 patients (395 per arm) to allow for a 15% drop-out rate. There will be an ongoing review of recruitment, sample size assumptions and dropout rates by the DMEC which will guide the TMG as to whether continuing recruitment to 90% power is feasible.

In May 2015 the recruitment target of 670 was met and the sample size was increased to 790 patients. Recruitment extended for 6 months, until November 2015.

13.2. Statistical Data Analysis

The primary outcome measure is the clinical hernia rate at 2 years. The number of clinical hernias at 2 years in the two treatment groups (biological mesh and control) will be compared using a chisquared test. Treatment effects will be expressed as a relative risk with 95% confidence interval. Any categorical secondary outcome measures (e.g. radiological hernia rate, re-operation rate, infection rates) will be analysed in the same way as the primary outcome. Continuous data (e.g. EuroQoL EQ-5D, pain scores) will be analysed using an independent 2-sample t-test (or the non-parametric equivalent as appropriate) at each time point, with the 2 year data considered the main analysis time point. Since data is being collected over multiple time points, longitudinal plots of the continuous data will be produced for visual presentation of the data, and a repeated measures analysis will be performed across all time points.

All analyses will be intention to treat, whereby patients will be analysed according to the treatment group to which they were randomised regardless of whether they complied with this treatment. All p-values will be 2-tailed and a p-value of <0.05 will be considered statistically significant.

The only planned subgroup analyses with be to compare the effect of biological mesh depending on stoma site (ileostomy or colostomy); surgical incision (reopening of midline wound or stoma site only); and skin closure type (primary or secondary). Subgroup analyses will employ a test of interaction to explore whether there is evidence that the treatment effects differ across subgroups. As with all subgroups analyses these will be interpreted with caution, and will be considered hypothesis generating.

13.3. Exploratory Data Analysis

ROCSS

An exploratory analysis will compare the radiological hernia rate at 1 year with clinical hernia rate at 2 years. This will provide useful information on the value of using a CT scan as an early diagnostic tool of herniation, which could then be used in future abdominal wall studies as a surrogate endpoint for clinical hernia. Correlation between CT and clinical hernia rates will be calculated as follows:

- The proportion of false negatives i.e. clinical but not radiological hernias
- The proportion of false positive i.e. radiological but not clinical hernias (at 2 years)

An additional analysis will correlate patient reported symptoms at the closed stoma site to clinical examination and CT findings.

14.Data Monitoring

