ROCSS: Reinforcement of Closure of Stoma Site

A randomised controlled trial of reinforcement of closure of stoma site using a biological mesh

A randomised controlled trial from the West Midlands Research Collaborative

Protocol v8.0

12th January 2021

Protocol Summary

The ROCSS Trial was completed with 2 year follow up and published in The Lancet in 2020. A short summary is below:

Methods

ROCSS took place in 37 hospitals across three European countries (35 UK, one Denmark, one Netherlands), patients aged 18 years or older undergoing elective ileostomy or colostomy closure were randomly assigned using a computer-based algorithm in a 1:1 ratio to either biological mesh reinforcement or closure with sutures alone (control). Training in the novel technique was standardised across hospitals. Patients and outcome assessors were masked to treatment allocation. The primary outcome measure was occurrence of clinically detectable hernia 2 years after randomisation (intention to treat). A sample size of 790 patients was required to identify a 40% reduction (25% to 15%), with 90% power (15% drop-out rate).

Findings

Between Nov 28, 2012, and Nov 11, 2015, of 1286 screened patients, 790 were randomly assigned. 394 (50%) patients were randomly assigned to mesh closure and 396 (50%) to standard closure. In the mesh group, 373 (95%) of 394 patients successfully received mesh and in the control group, three patients received mesh. The clinically detectable hernia rate, the primary outcome, at 2 years was 12% (39 of 323) in the mesh group and 20% (64 of 327) in the control group (adjusted relative risk [RR] 0.62, 95% CI 0.43–0.90; p=0.012). In 455 patients for whom 1 year postoperative CT scans were available, there was a lower radiologically defined hernia rate in mesh versus control groups (20 [9%] of 229 vs 47 [21%] of 226, adjusted RR 0.42, 95% CI 0.26–0.69; p<0.001). There was also a reduction in symptomatic hernia (16%, 52 of 329 vs 19%, 64 of 331; adjusted relative risk 0.83, 0.60–1.16; p=0.29) and surgical reintervention (12%, 42 of 344 vs 16%, 54 of 346: adjusted relative risk 0.78, 0.54–1.13; p=0.19) at 2 years, but this result did not reach statistical significance. No significant differences were seen in wound infection rate, seroma rate, quality of life, pain scores, or serious adverse events.

Interpretation

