4.2. Secondary Objectives

The secondary objectives of the ROCSS trial are to:

- Assess radiological hernia rates at one year post randomisation.
- Assess surgical re-intervention rates.
- Assess the frequency of wound infections and seroma associated with the mesh.
- Assess the impact of the mesh on a patient's quality of life and any pain experienced. Quality
 of life is an important secondary outcome measure, as the re-operation rate may be low, as
 even if a clinical hernia is diagnosed, the decision for surgical re-intervention has to take into
 account the patient's age, any co-morbidities and patient preference.
- Determine the cost effectiveness of the mesh insertion in stoma site closure and management of subsequent hernias.
- Conduct an exploratory analysis to investigate the CT scan as an early surrogate marker of late clinical herniation. Radiological hernia rate at one year post randomisation will be compared with the clinical hernia rate at two years to assess the value of using a CT scan as an early diagnostic tool of herniation. This will identify to other investigators that this is a potential area of clinical need and allow earlier reporting of future studies.

5. Outcome Measures

The outcome measures of the phase III trial will be:

Primary outcome

1. Rate of clinically detectable hernias at two years post-randomisation.

Secondary outcome measures

- 1. Radiological hernia rate at one year post-randomisation. An exploratory analysis will also compare radiological hernia rate at 1 year with clinical hernia rate at 2 years to assess the value of using a CT scan as an early diagnostic tool of incisional hernias.
- Incidence of developing a symptomatic hernia evaluated at 12 and 24 months postrandomisation. The clinical detection of hernias defined by palpable fascial defects, and global weaknesses around closed stoma sites without palpable fascial defects, will be recorded. Patient-reported hernia symptoms including a local lump or pain at the site of the stoma closure will also be collected.
- 3. Surgical re-intervention rates at 2 years post-randomisation.
- 4. Surgical complications, including wound infections at 30 days post-operatively and at 1 year post-randomisation, and seroma formation at 1 year post-randomisation.
- 5. Quality of life assessed using EuroQol EQ-5D at baseline, 30 days post-operatively, 12 and 24 months post-randomisation.

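### Section 13.3 raises 1-year CT as a possible surrogate endpoint, but the two discordance proportions it fixes cannot show whether CT carries the mesh effect on clinical hernia

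*Protocol*

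**What the plan says.** The surrogate purpose appears in three places in the protocol. Section 4.2 sets the objective: "Conduct an exploratory analysis to investigate the CT scan as an early surrogate marker of late clinical herniation". It adds that the result should "allow earlier reporting of future studies". Section 1.7 makes a similar statement, and section 13.3 says the analysis would inform the use of CT, "which could then be used in future abdominal wall studies as a surrogate endpoint for clinical hernia".

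The method is short. Section 4.2 says "Radiological hernia rate at one year post randomisation will be compared with the clinical hernia rate at two years". Section 13.3 says "Correlation between CT and clinical hernia rates will be calculated as follows" and then lists two items. The first is "The proportion of false negatives i.e. clinical but not radiological hernias"; the second is the converse, radiological hernias that are not clinical at 2 years. Neither item mentions randomised arm, and no threshold or decision rule is given.

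Section 13.2 separately has radiological hernia compared between arms by the same method as the primary outcome, as a relative risk with a 95% confidence interval. The Findings paragraph of the Protocol Summary reports both results: on CT "20 [9%] of 229 vs 47 [21%] of 226, adjusted RR 0.42", and clinically "12% (39 of 323) in the mesh group and 20% (64 of 327) in the control group", with an adjusted relative risk of 0.62. Section 18 repeats both relative risks. No section connects the two estimates to the surrogate question.

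**The concern.** A trial can be reported early on a surrogate only if the between-arm effect on the surrogate predicts the between-arm effect on the outcome it replaces. Agreement between CT and clinical examination in individual patients is a different property. A test can agree well with the clinical finding overall and still distort the treatment effect if its errors fall differently in the two arms. That is conceivable here, because a mesh might change what is visible on CT relative to what is palpable.

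Section 13.3 therefore names a purpose, possible surrogate use, that its stated metrics cannot serve. If a later reader took good agreement as support for CT as an endpoint, future abdominal wall trials could be designed and reported on a CT effect whose relation to the clinical effect had not been examined.

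**Working it through.** **Inputs** (Protocol Summary, Findings). Clinical hernia at 2 years: 39/323 mesh, 64/327 control; adjusted RR 0.62 (95% CI 0.43 to 0.90). CT hernia at 1 year: 20/229 mesh, 47/226 control; adjusted RR 0.42 (0.26 to 0.69). The correlation between the two log RRs is not given and is assumed below. No cross-tabulation of CT against clinical result is given.

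**1. Reproduce the reported effects.**
- Clinical: (39/323)/(64/327) = 0.617, crude log-scale 95% CI 0.427 to 0.891.
- CT: (20/229)/(47/226) = 0.420, CI 0.257 to 0.685.

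Both match the adjusted values. The crude risk differences are 7.5 and 12.1 percentage points in favour of mesh.

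**2. Can overall discordance identify the CT effect?** Keep the clinical counts as observed and assume, for illustration, 20 false negatives and 20 false positives in total. Overall sensitivity is 1 − 20/103 = 81%. In each arm, CT positives = clinical hernias − false negatives + false positives.
- All false negatives in mesh and all false positives in control: mesh 39 − 20 = 19, control 64 + 20 = 84. CT RR = (19/323)/(84/327) = 0.23.
- The reverse split: mesh 39 + 20 = 59, control 64 − 20 = 44. CT RR = (59/323)/(44/327) = 1.36.

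The clinical RR is 0.62 throughout. With 30 and 30 (sensitivity 71%) the range is 0.10 to 2.05. These are extreme splits, not likely ones. They show that the two proportions, without arm, are compatible with a CT effect that overstates, preserves or reverses the clinical effect.

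**3. The comparison that is not planned.**
- Ratio of adjusted RRs: 0.42/0.62 = 0.68.
- SE of log RR from the reported intervals: clinical [ln 0.90 − ln 0.43]/3.92 = 0.188; CT [ln 0.69 − ln 0.26]/3.92 = 0.249.
- SE of the log ratio = √(0.188² + 0.249² − 2ρ × 0.188 × 0.249).

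| Assumed ρ | 95% CI for the ratio | p |
|---|---|---|
| 0 | 0.37 to 1.25 | 0.21 |
| 0.3 | 0.40 to 1.14 | 0.14 |
| 0.5 | 0.44 to 1.05 | 0.08 |
| 0.7 | 0.48 to 0.96 | 0.03 |

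**4. What overall rates would show.** Both arms together: CT 67/455 = 14.7%, clinical 103/650 = 15.8%. These are close. By arm, CT against clinical is 8.7% v 12.1% with mesh and 20.8% v 19.6% in control. Overall similarity therefore says little about similarity of effects. The denominators differ, so these are not paired comparisons.

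**The case against.** The other side has several fair points.

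- **The analysis is exploratory and its first aim is diagnostic.** The sentence in section 13.3 names the diagnostic value of CT first, and false negatives and positives are ordinary metrics for that. The surrogate clause is conditional. This stands and limits the point to that clause. Section 4.2, however, also makes the surrogate marker the subject of the analysis and gives earlier reporting of future studies as its use.
- **Pooling is not stated.** A reader might infer that discordance is to be pooled over both arms. Section 13.3 is silent on arm, and a separate analysis plan, not available here, could tabulate by arm. The silence alone is no fault. What remains is that the protocol states a method for a surrogate purpose and includes no comparison of effects.
- **No pass criterion exists.** A reader might infer that a CT which overstates the mesh effect would be approved. The protocol sets no rule by which CT passes or fails. The supportable statement is that the listed metrics could not detect such distortion.
- **The two effects are not hidden.** Section 13.2 plans both relative risks, and the Protocol Summary and section 18 report them. Only their comparison, and its link to surrogate use, is absent.
- **The data do not establish that CT exaggerates.** A reader might infer that trials sized on CT would chase an effect patients do not get. Taking both sets of rates as true, 90% power needs about 180 per arm on CT rates and 496 on clinical rates. That contrast treats two uncertain point estimates as fact. Treating the samples as independent, the shift between CT and clinical rates has z of about 1.3 in mesh and 0.35 in control. The ratio interval includes 1 unless the correlation is high.
- **Timing.** Version 8.0 postdates publication of the two-year results. Any addition now is post hoc and must say so. The surrogate wording nevertheless remains in the current text and is addressed to future trials.

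**Conclusion.** The point holds in a limited form. Sections 1.7, 4.2 and 13.3 put 1-year CT forward as a possible surrogate, but the proportions fixed in 13.3 describe agreement in individuals. Without arm, and without a comparison of the two relative risks already planned in 13.2, they cannot show whether CT carries the mesh effect.

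The reported effects differ in point estimate, with a ratio of 0.68, but not conclusively. The interval depends on an assumed correlation, and the estimates come from 455 and 650 participants with unknown overlap. The documents support neither that CT overstates the effect nor that it preserves it. The primary analysis and the sample size are untouched. This is a minor point and a cheap improvement.

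**What to change.** In section 13.3, with matching lines in 4.2 and 5, add for participants who have both the 1-year CT and the 2-year clinical assessment:

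1. CT/clinical discordance reported separately by randomised arm.
2. The mesh relative risk on CT and on clinical hernia in these same participants, and their ratio with a bootstrap 95% CI. Resampling participants captures the correlation that had to be assumed above.
3. A label of exploratory and, because the two-year results are known, post hoc.

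A non-significant difference should not be read as agreement. Unless the interval is narrow enough to support similar effects, limit the conclusion to CT as an early predictor or diagnostic tool in individual patients, and drop the surrogate-endpoint wording in 1.7, 4.2 and 13.3.

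The cost is a few lines and one table from data already held. At most 455 participants can contribute, so the interval may well be wide. The real downside is that the surrogate statement may have to be weakened.
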